8.2 Serious adverse event reporting

Serious adverse events (SAEs) are adverse events where at least one of the following is true:

- The event results in death
- The event is life-threatening
- The event requires or prolongs hospitalization
- The event results in permanent disability or incapacity
- The event is a congenital abnormality / birth defect
- The event is medically important

In the case of a serious adverse event, the investigator must immediately fax the signed and dated Serious Adverse Event case report form, accompanied by copies of all examinations, to the designated medical monitor.

Medical and scientific judgment should be exercised in deciding whether expedited reporting is appropriate in *other* situations, such as important medical events that may not be immediately life-threatening or result in death or hospitalization but may jeopardize the subject or may require intervention to prevent one of the other outcomes listed in the above definition.

8.3 Follow-up of Adverse Events and Serious Adverse Events

The investigator should take all appropriate measures to ensure the safety of the subjects. The outcome of any adverse event (clinical signs, laboratory values, etc.) should be followed up until they return to normal or until stabilization of the patient's condition

9. Quality Control and Data management

Data management will be performed by the Data Coordinating Center. Subject identifiers will be eliminated and study subject numbers only will be used during data collection in the electronic case report forms to ensure compliance with study confidentiality and HIPAA standards. All study data will be maintained in strict confidentiality at the Data Coordinating Center. Quality control will be performed by both Coordinating and Data Management Centers. GCP standards will be followed. Monitors will evaluate data collection procedures, and data entry procedures will be defined by the Data Coordinating Center. Details on data collection and cleaning are shown in subsequent section. A Data Monitoring Committee (DMC) and a charter will be established. Any published data will remove all patient identifiers and patients will only be numerically listed in study reports.

9.1 Data Collection and Database Management

Data will be collected on standardized Case Report Forms (CRFs) using an online electronic data capture system (eCRFs). Individually assigned user IDs and passwords will be required to gain access to the system and access will be controlled based on role in the study. Extensive online data edits will be programmed as part of the electronic data captures system. Other data cleaning procedures will be applied as appropriate.

Adverse events will be coded using the most current version of MedDRA.

Concomitant medication use will be collected by drug class for commonly prescribed cardiovascular medications.

A separate Data Management Plan will provide details of the data collection, coding, cleaning and archival processes.

9.2 Site training and monitoring

Prior to study initiation, all investigators and research coordinators will be trained in the study protocol at a central investigators meeting. Each clinical site will be visited by trained clinical monitors at least once during the study to make sure that study protocol procedures are being followed, consent is being

obtained per regulation and data are being collected contemporaneously and accurately. Clinical monitoring visits will be scheduled as needed thereafter. Any serious complications of the implant procedure will be reviewed by the DMC and a summary of the failures and complications will be presented to the DMC at each meeting.

10. Assessment of Non-Inferiority Hypothesis and Data Analysis

This study was designed based on a non-inferiority hypothesis, with an overall type I error rate of 0.025 (1-sided). The non-inferiority margin is 1.5%.

10.1 Expected event rates

See section 5.1 for case mix assumptions. For Warfarin, the 30-day primary event rate is estimated to be 3.51 % based on the continuous Warfarin arm of the BRUISE control study⁽³⁾. For Edoxaban, we estimate the primary endpoint rate to be 0.5%. In the Danish study by Kirkfeldt⁽⁴⁾, major perioperative hematomas requiring re-intervention was 0.2% for new implants and 0.1% for generator changes. In this study, 26.6% of implants were ICDs and 73.4% were pacemakers. In the report by Dewland from the NCDR registry, ICD hematoma rates were estimated at 0.8% for new implants. Using the case mix assumptions in section 5.1, 30% new ICDs, 20% new pacemaker implants, 30% generator changes only, and 20% pulse generator changes and lead revisions, the estimate is more conservative (lower).

Details of this calculation and comparison to other studies can be found in Appendix A

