RATIONALE	Perioperative bleeding is a risk of cardiovascular implantable device insertion or replacement procedures. Bleeding complications predispose patients to interruption of OAC therapy, use of reversal agents, infection, and re-operation and prolong hospital stays. In patients with non valvular atrial fibrillation, interrupted Edoxaban therapy may offer safety and efficacy that is non inferior to continuous Warfarin therapy during these procedures
STUDY DESIGN	This is a prospective randomized comparative evaluation of Edoxaban and Warfarin for safety and efficacy in perioperative use in patients with non-valvular atrial fibrillation undergoing clinically indicated implantation or replacement of cardiovascular implantable electrical devices. This study is a randomized, open label, active-controlled trial with an open-label safety extension, designed to compare local and systemic bleeding within 30 days of cardiac rhythm device implant among patients randomized to continuous Warfarin or interrupted (<24 hours) Edoxaban. The study will have three phases; a run in phase to establish stable Warfarin therapy, an acute open label 30-day phase when patients will be randomized in a 1:1 ratio to receive interrupted Edoxaban or continuous Warfarin, which will be followed by an open label follow up phase for an additional 5 months for safety monitoring. Drug transitions will be performed according to approved drug labeling.
PRIMARY OBJECTIVE	The primary objective is to compare the rates of local and systemic bleeding in patients randomized to Edoxaban compared to patients randomized to continuous Warfarin in within 30 days of cardiac rhythm device implant with concomitant non-valvular AF.
SECONDARY OBJECTIVES	The secondary objectives are to compare the rates of thrombotic events (embolism or stroke) and MACE events through 6 months following the procedure in the Edoxaban and Warfarin groups.

NUMBER OF PATIENTS	A maximum of 400 patients will be enrolled

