In patients with non-valvular AF on OAC therapy with concomitant bradyarrhythmias or tachyarrhythmias warranting insertion or replacement of a CIED, an interrupted Edoxaban regimen without bridging anticoagulation is hypothesized to show comparable safety and efficacy to continuous Warfarin therapy for peri-procedural anticoagulation.

3. Objectives

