4.2.4 Secondary endpoint evaluation

The secondary endpoint of superiority for peri-procedural bleeds will be assessed using the same methodology as the primary endpoint, except that the test will be for superiority. If the study does not meet the non-inferiority endpoint, superiority will not be assessed. The overarching goal is to reduce peri-procedural bleeds without causing an increase in stroke. Thrombi may form slowly though clinical presentation may occur months later. Considering events through 6 months post procedure helps to ensure that the interruption of Edoxaban for the procedure does not result in an increase in late-occurring thrombi or other safety issues.

5. Study Population

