10.2 Sample size calculation (Appendix B)

It is possible, due to the low event rate in the Edoxaban arm and small sample size, that we could see no events in this arm. Thus, these sample size calculations are based on absolute risk differences rather than relative risk differences. Assuming event rates for Warfarin and Edoxaban of 3.51% and 0.5%, respectively, 300 total patients provides approximately 80% power to detect non-inferiority (margin 1.5%).

This study is a randomized, open label, active-controlled trial with an open-label safety extension, designed to compare local or systemic bleeding within 30 days of cardiac rhythm device implant for non-valvular AF among patients randomized to continuous Warfarin or interrupted Edoxaban. The DMC will review a formal interim analysis of the first 200 patients. Based on this analysis the DMC will make a recommendation about whether the study should be stopped or continued as planned. They may recommend that the study:

1. Be terminated for futility
2. Enroll an additional 100 patients in part II
3. Enroll an additional 200 patients in part II

Details about the criteria for this decision will be included in an interim statistical analysis plan and/or the DMC charter prior to the first data safety review. Because there is no opportunity to stop for efficacy after the first 200 patients, no type I error adjustment for the final analysis is necessary.

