Appendix B: Details of event rate assumptions

Calculation of Major Bleed Rate Assumption							
BRUISE-CONTROL Continuous Warfarin							
	Patients	% mITT	% ITT	Bleeds	% of Row		
N - ITT	343			12	3.50%		
Did not have procedure	8			0	0.00%		
Had procedure (mITT)	335	100.00%	97.67%	12	3.58%		
						Assumed Distribution	Weight Comp.
New Implant	156	46.57%	45.48%	5	3.21%	50%	
ICD	98	29.25%	28.57%	4	4.08%	30%	1.22%
PM	58	17.31%	16.91%	1	1.72%	20%	0.34%
Replacement / Revision	179	53.43%	52.19%	7	3.91%	50%	
Pulse generator change only	106	31.64%	30.90%	2	1.89%	30%	0.57%
Pulse generator change - plus*	73	21.79%	21.28%	5	6.85%	20%	1.37%
						Weighted Average Total	3.51%
*Additional procedure including repositioning or adding a lead, device pocket revision, upgrade from PM to ICD							
RE-LY							
	D110		D150		Warfarin		
	# surgeries	# bleed	# surgeries	# bleed	# surgeries	# bleed	% bleed
Urgent surgery	107	19	141	25	111	24	21.62%
Major surgery	473	29	511	33	498	39	7.83%
Elective surgery	1380	38	1405	53	1447	48	3.32%
Minor surgery	424	8	435	14	436	8	1.83%
Total	2384		2492		2492		
Major + Minor + Elective					2381	95	3.99%
Other trial overall major bleed rates							
	Bleed Rate	N	% Total Pts	Wt. Comp.			
RE-LY	4.6%	1558	19.0%	0.0088			
Yokoshiki	5.1%	59	0.7%	0.0004			
Denmark - haematoma	2.3%	5918	72.3%	0.0169			
Kutinsky (no drug)	8.7%	630	7.7%	0.0067			
Milic	4.8%	20	0.2%	0.0001			
Total (Weighted Average %)		8185		3.28%

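### Does the 0.5% Edoxaban bleeding rate, on which the 80% power rests, oblige the plan to change its sample size?

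*Combined protocol and SAP*

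**What the plan says.** Section 10.1 takes the Warfarin rate, 3.51%, from the continuous-Warfarin arm of BRUISE CONTROL, re-weighted to the expected case mix in Appendix B. For the other arm it says "For Edoxaban, we estimate the primary endpoint rate to be 0.5" per cent. Beside that figure it cites a Danish national cohort, in which "major perioperative hematomas requiring re-intervention was 0.2% for new implants and 0.1% for generator changes", and a US registry rate of 0.8% for new ICDs.

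Section 10.2 gives the sizing statement: "Assuming event rates for Warfarin and Edoxaban of 3.51% and 0.5%, respectively, 300 total patients provides approximately 80% power to detect non-inferiority (margin 1.5"%). The Synopsis sets the ceiling: "A maximum of 400 patients will be enrolled". After an interim look at 200 patients, section 10.2 lets the DMC recommend stopping for futility, adding 100 or adding 200. The criteria are left to an interim SAP or the DMC charter.

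The plan speaks of the expected effect in two ways. The closing paragraph of section 2 says "an interrupted Edoxaban regimen without bridging anticoagulation is hypothesized to show comparable safety and efficacy to continuous Warfarin therapy". Earlier in section 2, and in section 4.2.4, the stated expectation is a reduction in bleeding. Superiority is tested only after non-inferiority: "If the study does not meet the non-inferiority endpoint, superiority will not be assessed".

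**The concern.** The assumed ratio is 0.5/3.51 = 0.14, an 86% cut in bleeding. Three things make that look unsafe.

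- **Endpoint and population.** The Danish figures count only hematomas that needed re-intervention, in what section 1 calls the general CIED population. The definition in section 4.2.1 also counts a hematoma that prolongs the stay or interrupts anticoagulation. The Warfarin rate, by contrast, comes from an anticoagulated trial arm.
- **Appendix B.** Its RE-LY block sets two columns, D110 and D150, beside Warfarin. Their bleeding rates are close to Warfarin's, and none is below 1.89%.
- **Direction.** Section 10.1 describes its case-mix estimate as lower and therefore conservative. If that refers to Edoxaban, a lower rate raises power and is the optimistic direction. If it refers to Warfarin (3.51% after weighting against 3.58% among patients who had the procedure), the remark is right. The sentence does not say which.

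At stake is the primary conclusion. If Edoxaban bleeds nearly as often as Warfarin, a trial of 300 to 400 patients would probably miss the margin. Superiority would then not be tested, and a drug with similar bleeding would be reported as not shown to be non-inferior.

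**Working it through.** **Inputs.** Warfarin rate pW = 3.51% and Edoxaban rate pE = 0.5% (10.1); margin 1.5 points and one-sided 0.025 (section 10); 1:1 allocation (4.1); 300 patients (10.2) or 400 (Synopsis).

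**Step 1: reproduce the 80%.** Normal formula, per arm:

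n = (1.96 + 0.842)² × [pW(1 − pW) + pE(1 − pE)] / (0.015 + pW − pE)²

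= 7.849 × (0.03387 + 0.00498) / 0.0451² = 149.9, so 150 per arm and 300 in all.

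An exact unconditional test with score ordering (maximum size 0.0249 at both sample sizes) gives 79.6% at 150 per arm. The plan's figure stands.

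**Step 2: check the support for 0.5%.** Weight the rates cited in 10.1 by its case mix (30% new ICD, 20% new pacemaker, 30% generator change only, 20% generator change plus lead work). No rate is cited for the last group, so 0.1% to 0.8% is assumed:

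0.30 × 0.8 + 0.20 × 0.2 + 0.30 × 0.1 + 0.20 × (0.1 to 0.8) = 0.33% to 0.47%.

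So 0.5% follows from the cited rates, rounded slightly upward. The weakness is what those rates measure.

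**Step 3: RE-LY columns of Appendix B.**

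| Rows | D110 | D150 | Warfarin |
|---|---|---|---|
| Minor | 8/424 = 1.89% | 14/435 = 3.22% | 8/436 = 1.83% |
| Elective | 38/1380 = 2.75% | 53/1405 = 3.77% | 48/1447 = 3.32% |
| Major + elective + minor | 75/2277 = 3.29% | 100/2351 = 4.25% | 95/2381 = 3.99% |

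On the three-row total the ratios to Warfarin are 0.83 (95% CI 0.61 to 1.11) and 1.07 (0.81 to 1.40).

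**Step 4: power if 0.5% is wrong, Warfarin at 3.51%.**

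| True Edoxaban rate | Exact, 300 / 400 | Normal formula, 300 / 400 |
|---|---|---|
| 0.5% (plan) | 80% / 92% | 80% / 90% |
| 0.8% (ICD registry rate in 10.1) | 68% / 83% | 71% / 83% |
| 1.89% (lowest RE-LY non-Warfarin rate) | 33% / 44% | 39% / 49% |
| 3.51% (equal) | 8% / 11% | 10% / 13% |

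The normal columns are Φ(distance/SE − 1.96). At 1.89% and 150 per arm, distance = 0.0312 and SE = √[(0.03387 + 0.01854)/150] = 0.01869, so Φ(1.669 − 1.96) = 38.6%. Eighty per cent power at 1.89% would need 7.849 × 0.05241 / 0.0312² = 422.6, that is 423 per arm or 846 in all.

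**Step 5: what can pass at 400.** At 200 per arm the exact test accepts 3 Edoxaban events against 7 on Warfarin, 5 against 10, and 6 against 12. Observed cuts of 50% to 57% are therefore enough at those counts. A true rate of 0.88% (a 75% cut) is where power falls to 80%; it is not a condition for success. No table with equal counts passes at either size.

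**The case for a change.** The strongest case for a change is that one thinly supported input carries the whole design and no sensitivity calculation is shown. The argument need not rely on RE-LY: at the plan's own 0.8% registry rate, 300 patients give 68% and 400 give 83%. Fixing 400 as the final size would cost at most 100 patients already within the ceiling.

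The arithmetic stands, and so does the criticism that 10.1 does not derive 0.5% for the section 4.2.1 endpoint in anticoagulated patients. Several parts are weaker:

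- The RE-LY rows are mixed surgery. The column labels are not expanded, and neither the bleed definition nor the interruption practice is given. Appendix B computes a percentage and a subtotal for Warfarin only, which fits a cross-check of 3.51% and not a comparison that was set aside. So 1.89% is a sensitivity value.
- The other-trial rows of Appendix B appear to mix definitions. The Danish row is 2.3%, against 0.1% to 0.2% for re-intervention in 10.1, and a no-drug row stands at 8.7%, above the Warfarin assumption.
- Sections 2 and 4.2.4 state an expected reduction in bleeding, and superiority is prespecified. The sentence on comparable safety is not the whole of the plan's hypothesis.
- The exact test is not named, so 33% and 44% belong to the score-ordered version. At 1.72%, the lowest procedure row in Appendix B and itself one Warfarin event in 58, power at 400 is 49% by that test but 54% by the normal formula.

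**Conclusion.** The 0.5% is optimistic and weakly justified, but nothing in the plan has to change. The power statement is true for its stated inputs, and the type I error of the non-inferiority test does not depend on the assumed rate. A wrong guess lowers the chance of success; it does not make a positive result unsafe.

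Each possible change is a trade-off or brings no gain. Fixing 400 patients, or resizing to 846, means enrolling more against a rate that the documents do not establish. The plan can already reach 400, which holds 83% power at 0.8%. Futility criteria are deferred to the interim SAP or DMC charter, where analysts can set them. Restating the aim as estimation is a choice for the sponsor. A derivation of 0.5%, a power range in 10.2, and wording that a missed margin is inconclusive would help a reader but would not alter the analysis or its result.

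The power figures assume Warfarin at 3.51%, 1:1 allocation, no losses, no futility stop and, for the exact values, score ordering. Over true Edoxaban rates of 0.5% to 1.89%, exact power runs from 80% to 33% at 300 patients and from 92% to 44% at 400. That range is the risk the sponsor has accepted.

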10.2 Sample size calculation (Appendix B)

It is possible, due to the low event rate in the Edoxaban arm and small sample size, that we could see no events in this arm. Thus, these sample size calculations are based on absolute risk differences rather than relative risk differences. Assuming event rates for Warfarin and Edoxaban of 3.51% and 0.5%, respectively, 300 total patients provides approximately 80% power to detect non-inferiority (margin 1.5%).

This study is a randomized, open label, active-controlled trial with an open-label safety extension, designed to compare local or systemic bleeding within 30 days of cardiac rhythm device implant for non-valvular AF among patients randomized to continuous Warfarin or interrupted Edoxaban. The DMC will review a formal interim analysis of the first 200 patients. Based on this analysis the DMC will make a recommendation about whether the study should be stopped or continued as planned. They may recommend that the study:

1. Be terminated for futility
2. Enroll an additional 100 patients in part II
3. Enroll an additional 200 patients in part II

Details about the criteria for this decision will be included in an interim statistical analysis plan and/or the DMC charter prior to the first data safety review. Because there is no opportunity to stop for efficacy after the first 200 patients, no type I error adjustment for the final analysis is necessary.

10.3 Analysis of the primary objective

The primary comparison of rates will be based on the Exact test. If appropriate given the event distribution, the Cochran–Mantel–Haenszel test will be performed as a supportive analysis, including the stratification factors.

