4.1 Overview

This study is a randomized, open label, active-controlled trial with a safety extension (follow-up phase). It is designed to compare bleeding, local or systemic, within 30 days of cardiac rhythm device implant (acute phase) for non-valvular AF among patients randomized to continuous Warfarin or interrupted

Edoxaban. Randomization will be stratified by device type and HAS-BLED score (≤ 2 or ≥ 3). Patients will be randomized in a 1:1 ratio to receive interrupted Edoxaban or continuous Warfarin. This study contains an internal pilot opportunity to adjust the sample size or terminate the study, and there will be an interim analysis of the primary endpoint when 200 patients have reached 30-days post procedure or withdrawn. Based on the primary outcome in these 200 patients, the study may:

[figure not shown]
- Enroll 200 additional patients (pacemaker capped at 100 patients, ICD capped at 150 patients)
- Enroll 100 additional patients
- Be terminated

The study design is outlined in Figure 1.

Figure 1:

Study Design Flow Chart

Study Timeline

- Seamless design, enrollment does not stop between phases
-  Opportunity to stop if Part I objectives are not met
- Minimal resource commitment to Part II if Part I objectives not met
- For Part II, all sites enrolling, experience should lead to improved data quality compared to Part I
- Phases analyzed separately (primary) and combined

Eligible subjects must be stable on a therapeutic dose of Warfarin (INR 2-3) for three weeks prior to randomization. If potential patients are taking an anticoagulant besides Warfarin, or otherwise not meeting this criteria, must be switched to Warfarin and complete 3 weeks of dosing with INRs in the therapeutic range (run-in period) at randomization.

Comment [s1]: Segment into two sentences.
Insert period

Comment [s2]: delete

Comment [s3]: delete

Comment [s4]: Insert

The final INR should be performed on the day of randomization, and the procedure should be scheduled a minimum of 5 days and at most 15 days after randomization. Once eligibility has been confirmed and informed consent has been obtained, patients will be randomized via an interactive secure web randomization system. Patients will be randomized in a 1:1 ratio to Edoxaban or Warfarin. Randomization will be blocked by HAS-BLED score, and based on a randomization list, which will be created prior to commencement of the study.

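### The supportive Cochran-Mantel-Haenszel test in Section 10.3 does not test the 1.5% margin, so it says nothing on non-inferiority unless it shows superiority

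*Combined protocol and SAP*

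**What the plan says.** The opening of Section 10 sets a non-inferiority hypothesis at one-sided 0.025 and states: "The non-inferiority margin is 1.5" percent. Section 10.2 says that the sample size calculations are "based on absolute risk differences rather than relative risk differences", because the Edoxaban arm might have no events. The synopsis names a one-sided exact test for non-inferiority.

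Section 10.3 makes an exact test the primary comparison. It then adds, if the event distribution allows, a CMH analysis: this "test will be performed as a supportive analysis, including the stratification factors". It gives no margin, no stratified risk difference and no confidence limit for that analysis.

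Section 10.4 separates the two hypotheses. For Warfarin minus Edoxaban, non-inferiority means a difference above -1.5%, and superiority means a difference other than zero. It defers further detail to a statistical analysis plan to be finalized before database lock.

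Section 4.1 says first that randomization is stratified by device type and HAS-BLED score, and later that it is blocked by HAS-BLED score, with no mention of device type.

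**The concern.** The standard CMH test asks whether the common odds ratio across strata equals 1. By the distinction drawn in Section 10.4, that is the superiority null, yet it stands under the non-inferiority objective. It is on a different scale from the primary analysis and does not use the margin.

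A supportive analysis should show whether the primary conclusion survives a reasonable change of method, here adjustment for the randomization factors. A non-significant CMH cannot show this. It could be read as reassurance when Edoxaban is worse, or as a contradiction when non-inferiority has been met. No other stratified analysis of the bleeding endpoint is specified, so the question of how the stratified estimate compares with the margin goes unanswered.

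**Working it through.** **Inputs.** Section 10.2: "Assuming event rates for Warfarin and Edoxaban of 3.51% and 0.5%, respectively". Section 10: margin 0.015, one-sided 0.025. Section 4.1: 1:1 allocation. Section 10.2: "300 total patients provides approximately 80% power to detect non-inferiority (margin 1.5" percent.

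**1. The plan's own figure.** With unpooled variance,

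n per arm = (1.960 + 0.842)² × [0.0351 × 0.9649 + 0.005 × 0.995] / (0.0351 − 0.005 + 0.015)²
= 7.849 × 0.03884 / 0.002034 = 149.9, so 150 per arm and 300 in total.

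Power at 300 is 80.0%. Full binomial enumeration of the Farrington-Manning score test gives 79.6%, and so does the exact unconditional version. The design therefore rests on a margin-shifted risk difference.

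**2. The two tests.** Let x and y be the bleeds on Edoxaban and Warfarin, with t = x + y, at 150 per arm.

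- Non-inferiority score test: z = (x/150 − y/150 − 0.015) / SE, with SE from the rates fitted under a difference of exactly 0.015.
- Mantel-Haenszel test, single stratum, no continuity correction: z = (x − t/2) / √[t(300 − t)/(4 × 299)].

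The margin appears only in the first. A single stratum is used because the documents give no sizes or rates by randomization stratum.

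**3. Two example outcomes (Edoxaban vs Warfarin).**

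| Bleeds | Non-inferiority test | Mantel-Haenszel test |
|---|---|---|
| 1 vs 5 | (−0.0267 − 0.015)/0.0183 = −2.27, one-sided p = 0.011, met | (1 − 3)/√1.475 = −1.65, two-sided p = 0.10 |
| 8 vs 5 | (0.0200 − 0.015)/0.0234 = 0.21, one-sided p = 0.58, not met | (8 − 6.5)/√3.120 = 0.85, two-sided p = 0.40 |

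Non-significance on the Mantel-Haenszel test goes with success in one case and clear failure in the other.

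**4. How often, at the plan's rates.** Enumerating all outcomes at 150 per arm:

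- non-inferiority met: 79.6%;
- Mantel-Haenszel significant in favour of Edoxaban: 47.6%, in every case with non-inferiority also met;
- non-inferiority met and Mantel-Haenszel non-significant: 79.6% − 47.6% = 32.0%.

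Among trials that meet non-inferiority, 32.0/79.6 = 40.2% would have a non-significant Mantel-Haenszel result. For 80% power the zero-null comparison would need 340 per arm, or 680 in total, against a maximum enrolment of 400.

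**5. Sparseness.** Expected bleeds at 300 patients are 150 × 0.0351 + 150 × 0.005 = 5.3 + 0.75, about 6. Assume, for illustration, four equal strata with equal rates. Each stratum then has 37.5 patients per arm and no events with probability (0.9649 × 0.995)^37.5 ≈ 0.217. The chance that at least one stratum is empty is 1 − (1 − 0.217)⁴ ≈ 62%.

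**The case against.** The case on the other side has several parts, and most of them stand.

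- **CMH can support non-inferiority.** A reader might infer that it never can. That is too strong. A result significant in favour of Edoxaban shows superiority, and in the enumeration this never occurred without the non-inferiority test also being met. The support runs in one direction only.
- **The decision does not rest on CMH.** The primary exact test carries the margin, and CMH is both supportive and conditional. Nothing in the documents says that a non-significant CMH will be read as non-inferiority, and Section 10.4 shows that its authors knew the distinction. A reader might infer that the primary conclusion is undermined; the documents do not support that.
- **It is not the only stratified analysis in the plan.** The hemoglobin ANCOVA in Section 10.4 also adjusts for the stratification factors. The gap concerns the bleeding endpoint only.
- **One striking figure says less than it seems to.** If Edoxaban were worse by exactly the margin (5.01% vs 3.51%), CMH would be non-significant in 90.6% of trials. This is low power against a small difference, not a rate of false claims: the margin-based test would be met in only 2.4% of such trials.
- **The 40% reflects superiority being harder to show than non-inferiority.** It does not mean that the primary result is wrong in those trials.
- **More detail is promised in a later analysis plan.** This carries less weight. Section 10.3 already names the method, so the later document would have to replace it, not merely elaborate it.

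**Conclusion.** The point holds in a limited form. The CMH test in Section 10.3 does not address the 1.5% margin and is informative on non-inferiority only when it shows superiority. The plan therefore has no stratified check of the bleeding endpoint against the margin. The primary test, margin, sample size and type I error are untouched.

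The size of the mismatch is 47.6% against 79.6% power, with about 40% of successful trials showing a non-significant CMH. These figures assume 150 per arm, the plan's event rates, a single stratum and no continuity correction. They illustrate the mismatch and do not describe the behaviour of the stratified test. The point also assumes the standard CMH null, since the documents define no margin-shifted version.

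The change is worth making because it substitutes an analysis that answers the primary question, using the same data and strata.

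**What to change.** In Section 10.3:

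- Replace CMH with a stratified risk difference over the randomization strata, using Mantel-Haenszel weights or the stratified Miettinen-Nurminen method. Compare the one-sided 97.5% lower bound for Warfarin minus Edoxaban with -1.5%.
- Keep the condition that the event distribution must allow the analysis, and state in advance what happens with sparse or zero-event strata, for example pooling them.
- Name the strata, after reconciling the two descriptions of randomization in Section 4.1.

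In Section 10.4, name CMH as the stratified companion to the superiority test, where its null is the right one.

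The cost is a small amount of extra specification and no new data. The drawback is that, with about 6 expected events, the stratified estimate may itself be fragile. It should stay supportive, and the sparse-stratum rule should be fixed before the data are seen.
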